3.1 Inclusion Criteria

1. Age \geq 18 years at enrollment (the time of informed consent, week -1)
2. Fasting TG levels \geq 500 mg/dL (\geq 5.7 mmol/L) at enrollment. If the fasting TG value is $<$ 500 mg/dL ($<$ 5.7 mmol/L) but \geq 350 mg/dL (\geq 4.0 mmol/L) up to two additional tests may be performed in order to qualify, and a single level \geq 500 mg/dL will permit enrollment.

OR

3. Fasting TG levels \geq 200 mg/dL (2.6mmol/L) with a hemoglobin A1C over 7%
4. Willing to maintain their customary physical activity level and to follow a diet moderate in carbohydrates and fats with a focus on complex carbohydrates and replacing saturated for unsaturated fats
5. Clinical diagnosis of lipodystrophy based on deficiency of subcutaneous body fat in a partial fashion assessed by physical examination, and low skinfold thickness in anterior thigh by caliper measurement: men (\leq 10mm) and women (\leq 22 mm), plus one of the following:

a) Genetic diagnosis of familial PL (e.g., mutations in LMNA, PPAR- γ , AKT2, or PLIN1 genes)

OR

b) Family history of familial PL or abnormal and similar fat distribution PLUS 1 minor criterion (below), OR

c) 2 minor criteria (below) in the absence of genetic diagnosis of family history

MINOR Criteria

- a. Diabetes mellitus with requirement for high doses of insulin, eg, requiring \geq 200 U/day, \geq 2 U/kg/day, or currently taking U-500 insulin
- b. Presence of acanthosis nigricans on physical examination
- c. History of polycystic ovary syndrome (PCOS) or PCOS-like symptoms (hirsutism, oligomenorrhea, and/or polycystic ovaries)
- d. History of pancreatitis associated with hypertriglyceridemia
- e. Evidence of non-alcoholic fatty liver disease
 - Hepatomegaly and/or elevated transaminases in the absence of a known cause of liver disease or
 - Radiographic evidence of hepatic steatosis (e.g., on ultrasound or CT)

6. Satisfy one of the following:

- a) Females: Non-pregnant and non-lactating; surgically sterile (e.g., tubal occlusion, hysterectomy, bilateral salpingectomy, bilateral oophorectomy), post-menopausal (defined as 12 months of spontaneous amenorrhea in females >55 years of age or, in females ≤55 years, 12 months of spontaneous amenorrhea without an alternative medical cause and follicle-stimulating hormone (FSH) levels in the postmenopausal range for the laboratory involved), abstinent*, or if engaged in sexual relations of child-bearing potential, patient is using an acceptable contraceptive method (refer to Section 7.4.1) from time of signing the informed consent form until at least 13 weeks after the last dose of Study Drug administration.
- b) Males: Surgically sterile, abstinent*, or if engaged in sexual relations with a female of child-bearing potential, patient is utilizing an acceptable contraceptive method (refer to Section 7.4.1) from the time of signing the informed consent form until at least 13 weeks after the last dose of study drug administration.

** Abstinence is only an effective method of birth control when this is the preferred and usual lifestyle of the patient. Periodic abstinence (e.g., calendar, ovulation, symptothermal, post-ovulation methods), declaration of abstinence for the duration of a trial and withdrawal are not acceptable methods of contraception.*

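### Inclusion criterion 3 prints its triglyceride threshold as 200 mg/dL and as 2.6 mmol/L, and by the protocol's own conversions these are different values (200 mg/dL is about 2.3 mmol/L)

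*Combined protocol and SAP*

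**What the plan says.** Section 3.1 of the combined protocol and SAP prints three triglyceride thresholds, each in two units.

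- Item 2, main threshold: "Fasting TG levels \geq 500 mg/dL (\geq 5.7 mmol/L) at enrollment".
- Item 2, lower limit for retesting: "350 mg/dL (\geq 4.0 mmol/L) up to two additional tests may be performed".
- Item 3, the alternative route, joined to item 2 by OR: at or above "200 mg/dL (2.6mmol/L) with a hemoglobin A1C over 7" percent.

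No other section restates the item 3 threshold in either unit. Section 7.9, which explains the choice of patients, mentions only those above 500 mg/dL and is silent on the item 3 route.

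**The concern.** The item 3 pair implies a different conversion factor from the two pairs directly above it, so at least one of its two numbers is wrong as printed. The figure sits in an entry criterion, so it acts as a decision rule and is not background text.

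The retest provision in item 2 starts at 350 mg/dL. A patient whose triglycerides lie a little above 200 mg/dL therefore has no route in except item 3, and for such a patient the answer depends on which of the two printed values is read. Entering a patient who breaches a criterion has consequences in the protocol: Section 7.8 lists entry-criteria violations among the reasons for withdrawal, and Section 7.2.1 treats any departure from the approved protocol as a deviation. A criterion that can be read two ways leaves both judgements open to dispute.

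**Working it through.** **Inputs, all from Section 3.1**

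- Item 2: 500 mg/dL printed with 5.7 mmol/L.
- Item 2: 350 mg/dL printed with 4.0 mmol/L.
- Item 3: 200 mg/dL printed with 2.6 mmol/L.

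**Step 1. Factor implied by each pair** (mg/dL divided by mmol/L). The range treats the mg/dL value as exact and the mmol/L value as rounded to one decimal.

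| Pair | Implied factor | Range from rounding |
|---|---|---|
| 500 and 5.7 | 500/5.7 = 87.7 | 500/5.75 = 86.96 to 500/5.65 = 88.50 |
| 350 and 4.0 | 350/4.0 = 87.5 | 350/4.05 = 86.42 to 350/3.95 = 88.61 |
| 200 and 2.6 | 200/2.6 = 76.9 | 200/2.65 = 75.5 to 200/2.55 = 78.4 |

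The first two ranges overlap. The third lies well below both.

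**Step 2. Try to reproduce the printed 2.6 mmol/L.** Divide 200 mg/dL by the item 2 factors:

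- 200/87.7 = 2.28 mmol/L
- 200/87.5 = 2.29 mmol/L
- over the whole range in step 1: 200/88.61 = 2.26 to 200/86.42 = 2.31 mmol/L

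To one decimal the result is 2.3 throughout. The printed 2.6 is not reproduced.

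**Step 3. Convert the other way.**

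- 2.6 × 87.7 = 228 mg/dL
- 2.6 × 87.5 = 227.5 mg/dL
- over the whole range: 2.6 × 86.42 = 225 to 2.6 × 88.61 = 230 mg/dL

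**Step 4. Size of the gap.** 228 − 200 = 28 mg/dL, and 28/200 = 14%.

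**Step 5. Could rounding account for it?** The smallest value that rounds to 2.6 is 2.55 mmol/L. With the smallest factor that the item 2 pairs allow, 2.55 × 86.42 = 220 mg/dL, still 20 mg/dL above the printed figure. Rounding cannot close the gap.

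**Step 6. Sensitivity to the usual factor.** The customary triglyceride factor is 88.57 mg/dL per mmol/L. The documents do not print it, so it is an assumption here. It gives 200/88.57 = 2.26 mmol/L and 2.6 × 88.57 = 230 mg/dL, a gap of 30 mg/dL or 15%. It agrees with the item 2 pairs to about 1% (500/88.57 = 5.65; 350/88.57 = 3.95). The conclusion does not rest on it.

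**Step 7. Is this a habit of the document?** No. The glucose thresholds that are given in both units agree with one another: 70 mg/dL with 3.9 mmol/L in Section 7.5.7 (70/3.9 = 17.9), and 270 with 15.0 and 240 with 13.3 in Section 7.5.8 (18.0 and 18.0). The item 3 pair is an isolated slip.

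**The case against.** The strongest reply is that there is really one cut-off with a faulty conversion beside it. In item 3 the at-or-above sign attaches only to the mg/dL value, whereas item 2 repeats it inside the brackets. The closing clause of item 2 decides enrolment on mg/dL alone. Triglycerides elsewhere are also in mg/dL: Section 2.1, Table 2 in Section 2.3.4, exclusion 8b in Section 3.2, the sample-size text in Section 5.1, and Section 7.9. Staff would probably apply 200 mg/dL. This stands as an argument about likely practice. It does not make the two numbers equal, and no sentence says that mg/dL governs.

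A reader might infer more than the documents support, in four ways.

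- **That prescreening from outside records in mixed units would misclassify patients.** Section 6.3.2 uses prescreening only to raise the chance that criteria will be met. Eligibility is tested at the NIH admission, with a lipid panel (Section 6.3.3). The one outside result that counts toward enrolment is LDL-C. Nothing shows an outside triglyceride value in mmol/L being used. At most, a prescreener who read only the bracket could turn someone away early.
- **That one misclassified patient would be a tenth of a sample of ten.** That is only 1/10 and would apply to any eligibility slip. The documents give no sign that anyone fell in the disputed band, which is narrow: about 200 to 228 mg/dL, with HbA1c over 7% and, by exclusion 8c, below 9.5%.
- **That the treatment comparison would be biased.** A patient in the band who entered would be randomised like any other (Section 4.1).
- **That the power is affected.** The Section 5.1 calculation uses a difference of 0.50 and an SD of 0.25 in log10 mg/dL with 5 patients per group. The entry threshold does not enter it.

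The figure 2.6 may also be 2.26 with a digit dropped. That is plausible, but the documents do not show it.

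**Conclusion.** The criterion is wrong as printed: its two values cannot both be the threshold. On the protocol's own conversions the discrepancy is about 28 mg/dL (14%), or 30 mg/dL (15%) if the factor 88.57 is assumed. The patients affected are those with HbA1c over 7% and fasting triglycerides from 200 to just under about 228 mg/dL.

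The arithmetic rests only on the two pairs in item 2 and on one-decimal rounding. The judgement that the practical effect is small rests on the consistent use of mg/dL elsewhere and on testing at a single centre. The documents do not settle which value was intended, and this review does not choose between them. Low severity.

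**What to change.** The sponsor should check item 3 against the master copy of the protocol and reconcile the two values so that the criterion states one threshold. If 200 mg/dL is the intended value, the bracket should read about 2.3 mmol/L. One added sentence in Section 3.1 should say which unit governs where both are printed. If anyone was screened with triglycerides between 200 and about 230 mg/dL under item 3, the study file should record which figure was applied.

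The cost is one number and one sentence in the next amendment. The design, sample size and analysis do not change.

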3.2 Exclusion Criteria

1. A diagnosis of generalized lipodystrophy
2. Current or history of autoimmune diseases (even with a diagnosis of PL) unless approved by the Investigator and Sponsor Medical Monitor
3. Acute pancreatitis within 4 weeks of enrollment
4. History within 6 months of enrollment of acute or unstable cardiac ischemia (myocardial infarction, acute coronary syndrome, new onset angina), stroke, transient ischemic attack, or unstable congestive heart failure requiring a change in medication
5. Major surgery within 3 months of enrollment
6. History of heart failure with New York Heart Association functional classification (NYHA) greater than Class II
7. Uncontrolled hypertension (blood pressure [BP] >160/100 mm Hg)
8. Any of the following laboratory values at enrollment:
 - a. Cardiac troponin T >ULN
 - b. Measured or estimated (in case of triglycerides > 400 mg/dL) LDL-C >130 mg/dL on maximal tolerated statin therapy
 - c. Hemoglobin HbA1c ≥9.5%
 - d. Hepatic:
 - i. Total bilirubin >ULN
 - ii. ALT >3.0 x ULN. Higher levels will be permitted after a safety review by a hepatologist, that includes no evidence of cirrhosis.
 - iii. AST >3.0 x ULN. Higher levels will be permitted after a safety review by a hepatologist, that includes no evidence of cirrhosis.
 - e. Renal:

[figure not shown]
- i. Persistently positive (2 out of 3 tests \geq trace positive) for blood on urine dipstick. In the event of a positive test eligibility may be confirmed with urine microscopy showing \leq 5 red blood cells per high power field (urine will be screened at admission and repeated if abnormal). If RBC are high every effort will be made to determine if the source is renal or benign, such as from menstrual bleeding. If the presence of RBC is determined to be from a non-renal source, the PI will make the decision to proceed with protocol testing and/or randomization.
 - ii. Two out of three consecutive tests \geq 1+ for protein on urine dipstick. In the event of a positive test eligibility may be confirmed by either a spot urine albumin to creatinine ratio $<$ 1000mg/g or a quantitative total urine albumin measurement of $<$ 1g/24 hrs (urine will be screened at admission and repeated if abnormal)
 - iii. Estimated creatinine clearance calculated according to the formula of Cockcroft and Gault $<$ 60 mL/min
 - f. Platelet count below 140,000 K/uL
 - g. Clinically significant (as determined by the Investigator or Sponsor) abnormalities on laboratory examination that will increase risk to the patient or interfere with data integrity
9. Uncontrolled hypothyroidism (abnormal thyroid function tests should be approved by the Investigator)
 10. History within 6 months of enrollment of screening of drug or alcohol abuse
 11. History of bleeding diathesis or coagulopathy or clinically significant abnormality in coagulation parameters at enrollment
 12. Active infection requiring systemic antiviral or antimicrobial therapy that will not be completed prior to enrollment
 13. Known history of or positive test for human immunodeficiency virus (HIV), hepatitis C or chronic hepatitis B
 14. Malignancy within 5 years, except for basal or squamous cell carcinoma of the skin or carcinoma in situ of the cervix that has been successfully treated
 15. Treatment with another investigational drug, biological agent, or device within one month of enrollment, or 5 half-lives of investigational agent, whichever is longer
 16. Unwilling to comply with contraceptive and lifestyle (diet/exercise) requirements
 17. Use of any of the following:
 - a. Use of metreleptin within the last 3 months prior to enrollment
 - b. Antidiabetic, lipid lowering, or atypical antipsychotic medication, unless on a stable dose for at least 3 months prior to enrollment
 - c. Insulin unless on a stable daily insulin dose regimen (\pm 20 %) for at least 4 weeks prior to enrollment
 - d. Use of nicotinic acid or derivatives within the last 4 weeks prior to enrollment
 - e. Systemic corticosteroids or anabolic steroids within 6 weeks prior to enrollment unless approved by the Investigator
 - f. Antihypertensive medication unless on a stable dose for at least 4 weeks prior to enrollment
 - g. Tamoxifen, estrogens or progestins unless on a stable dose for at least 4 months prior to enrollment and dose and regimen expected to remain constant throughout the study
 - h. Oral anticoagulants unless on a stable dose for at least 4 weeks prior to enrollment and regular clinical monitoring is performed
 - i. Prior exposure to ISIS 304801

- j. Anti-obesity drugs [e.g., the combination of phentermine and extended-release topiramate (Osymia, orlistat (Xenical), liraglutide [rDNA origin] injection (Saxenda) and lorcaserin (Belvig), phentermine, amphetamines, herbal preparations] within 12 weeks prior to screening
 - k. Any other medication unless stable at least 4 weeks prior to enrollment (occasional or intermittent use of over-the-counter medications will be allowed at Investigator's discretion)
18. Blood donation of 50 to 499 mL within 30 days or of >499 mL within 60 days
19. Have any other conditions, which, in the opinion of the Investigator or the Sponsor would make the patient unsuitable for inclusion, or could interfere with the patient participating in or completing the study

4. Study Design

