8. Magnetic Resonance Imaging (MRI) and Magnetic Resonance Spectroscopy (MRS): Hepatic, muscle and central body fat will be measured by magnetic resonance imaging (MRI) and magnetic resonance spectroscopy (MRS). Studies are performed on a 3T MRI scanner using phased-array coils. Hepatic and muscle fat fraction will be determined⁴⁸. Visceral and subcutaneous fat measurements will be obtained using standard T1 Spin Echo technique which presents fat as a bright signal that can be segmented for area and volume measurements. In addition, MRI scanning will be performed for angiography (without gadolinium), vessel wall, and endothelial function⁴⁹. Each subject will be asked to perform a hand-grip exercise to obtain arterial dimensions. Before entering the magnet, we shall measure the maximal force production while hand squeezing a nonmagnetic hand-grip device. Later in the magnet at roughly one quarter of his/her maximal force, we will obtain MR data before, during, and after this exercise. The use of the device will be continuously monitored and the subject will be able to switch hands if one hand becomes fatigued.
9. Carotid intima-media thickness (cIMT): cIMT is an established marker of coronary artery disease and cardiovascular risk. This is a non-invasive test using ultrasonography of the carotid arteries in the neck.
10. 7-point plasma glucose: Plasma glucose will be measured prior to each meal, 90 minutes after each meal, and at bedtime. Area under the curve for glucose will be calculated using the trapezoidal method.
11. Liver biopsy: An optional liver biopsy will be performed in patients at the initial visit and at the end of the open label extension period (after 12-16 months of exposure to ISIS 304801). Biopsies will be performed transcutaneously unless there is a clinical reason for another approach (e.g. transjugular). These biopsies are performed primarily for research purposes, although clinical data about the severity of non-alcoholic fatty liver disease (NAFLD) or non-alcoholic steatohepatitis (NASH) will be obtained as well. Patients will sign a research consent for each liver biopsy prior to the procedure. Patients will be allowed to refuse the biopsies and continue to participate in the rest of the study. Platelet count will be obtained prior to percutaneous liver biopsy, and the biopsy will not be

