performed if patients have evidence of coagulopathy unresponsive to vitamin K (INR >1.5) or low platelets (Platelets < 75,000 k/uL) which may place them at a potentially higher risk for bleeding. About half of the liver biopsy sample will be fresh frozen in liquid nitrogen and will be stored for molecular analyses and Metabolomics studies in collaboration with [name] at the University of Michigan.

Histologic analysis: Specimens will be graded for the severity of NAFLD/NASH pathology. Histological features of NAFLD/NASH will be studied using the validated NASH-CRN (NASH Clinical Research Network) scoring system (3). This scoring system comprises histological features, 4 of which [steatosis (0-3), lobular inflammation (0-3), hepatocellular ballooning (0-2) and fibrosis (0-3 with grade 1 divided in three categories as well)] are evaluated semi-quantitatively. NAFLD activity score (NAS) is the unweighted sum of steatosis, lobular inflammation and hepatocellular ballooning scores. Total of this together with the fibrosis score constitutes the total NASH score.

12. **Metabolomics:** Studies will be done in the Molecular Phenotyping Core of the Michigan Metabolomics and Obesity Center at the University of Michigan in collaboration with [name]. Plasma samples collected in the fasting state and liver biopsy samples will be extracted according to the method of Bligh and Dyer ⁵⁰ for analysis. Lipomic studies will include measurement of subclasses of lipids and fatty acid composition. Unbiased metabolomics studies of plasma will be conducted using LC/MS and GC/MS.

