7.6.3 Stopping Rule for Platelet Count Results

In the event of a confirmed platelet count less than 75,000/mm³ that is associated with major bleeding or clinically relevant non-major bleeding (defined below⁵³), dosing of a patient with study drug (ISIS 304801 or placebo) will be stopped permanently. The follow-up schedule for any events meeting this stopping criterion will be determined by the Investigator in consultation with the Sponsor Medical Monitor as needed.

In the event of any platelet count less than 25,000/mm³, or a platelet count less than 50,000/mm³ that occurs while the patient is on dosing at 300 mg every two weeks or 150 mg every week then dosing of a patient with Study Drug (ISIS 304801 or placebo) will be stopped permanently. Platelet count will be monitored daily until 2 successive values show improvement then monitored every 2-3 days until 2 successive values are > 75kmm³, then monitored every 1 week.

Administration of steroids is recommended for patients whose platelet count is less than $\leq 50K/mm^3$. Recovery in platelet count may be accelerated by administration of high dose steroids. Treatment guidelines for immune thrombocytopenia (Provan et al.; 2010) recommend Dexamethasone 40 mg daily for 4 days every 2-4 wk for 1-4 cycles; Prednis(ol)one 0.5-2 mg/kg/d for 2-4 weeks then taper; or Methylprednisolone 30 mg/kg/day for 7 days (**note:** may require continuation with oral steroids after methyl prednisolone).

In the event of a confirmed platelet count less than 75,000/mm³, and in the absence of major bleeding or clinically relevant non-major bleeding (defined below⁵³), dosing of a patient with study drug (ISIS 304801 or placebo) will be suspended temporarily until the platelet count has recovered to $\geq 100,000/mm^3$. If dosing is continued it should be at a reduced dose frequency of 300 mg every two weeks or a reduced dose of 150 mg per week. The suitability of the patient for continued dosing and the need for any modification to treatment

schedule (refer to Section 7.7) will be determined by the Investigator (in consultation with the Ionis Medical Advisor as needed) and will be based on factors such as the original rate of decline in the patient’s platelet count, whether any bleeding events were experienced by the patient, and the speed of recovery of platelet count upon holding of dosing.

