If after the first dosing re-challenge the platelet count again falls below 50,000/mm³, then dosing of the patient must be held until the platelet count again returns to at least 100,000/mm³. The suitability of the patient for continued dosing and the need for any further modification to treatment schedule or dose (refer to Section 7.7) will be re-examined by the Investigator (in consultation with the Sponsor Medical Monitor as needed) based on (at least) the factors mentioned above.

If after the second re-challenge the platelet count falls below 50,000/mm³ and is subsequently confirmed (see Section 7.5), dosing with Study Drug will be stopped permanently. The follow-up schedule for any events meeting this stopping criterion will be determined by the Investigator (in consultation with the Sponsor Medical Monitor as needed).

Following rechallenge platelet count should be tested every week until count is stable.

Any unreportable platelet count result must be rechecked and determined not to have met a stopping rule before dosing can continue.

If there is no reportable platelet count within 14 days of the last platelet count, the investigator will contact the patient to hold dosing until a new platelet count is obtained and reviewed.

Definition of Major Bleeding Events^{s3}:

1. Fatal bleeding, and/or
2. Symptomatic bleeding in a critical area or organ, such as intracranial, intraspinal, intraocular, retroperitoneal, intraarterial or pericardial, or intramuscular with compartment syndrome, and/or
3. Bleeding causing a fall in hemoglobin level of 20.0 g/L (1.24 mmol/L) or more within 24 hours, or leading to transfusion of two or more units of whole or red cells

Definition of Clinically Relevant, Non-Major Bleeding Events^{s3}:

1. Multiple-source bleeding
2. Spontaneous hematoma >25 cm²
3. Excessive wound hematoma (not injection site related)
4. Macroscopic hematuria (spontaneous or lasting >24 hours if associated with an intervention)
5. Spontaneous rectal bleeding; epistaxis, gingival bleeding, hemoptysis, hematemesis
6. Bleeding after venipuncture for >5 minutes

Actions in Patients With Low Platelet Count

Platelet count	Dosing Rules	Monitoring Rules
Normal range, >140K/mm ³	No action	Monitor every week unless otherwise specified

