100K/mm ³ - 140K/mm ³	Weekly 300 mg study drug administration	Monitor every 1 week unless otherwise specified Obtain additional lab tests if 2 occurrences of platelet count 100 K/mm ³ -- 140K/mm ³ or 1 occurrence of platelet count ≤ 100K/mm ³ **
75K/mm ³ - 100K/ mm ³	Permanently reduce dose frequency to 300 mg every 2 weeks	Monitor every 1week unless otherwise specified Obtain additional lab tests if 1 occurrence of platelet count ≤ 100K/mm ³ **
50K/mm ³ - 75K/mm ³	If occurs while on dose of 300 mg every 2 weeks or 150 mg every week then permanently discontinue Study Drug, otherwise dose pause. When platelet count returns to >100K/mm ³ restart dosing at dose frequency of 300 mg every 2 weeks or 150 mg weekly ₁ (in consultation with the Ionis Medical Advisor as needed).	Monitor every 2-3 days until two successive values are > 75K/mm ³ then monitor every 1 week Consider discontinuation of antiplatelet/agents/NSAIDS/anticoagulant medication Obtain additional lab tests if 1 occurrence of platelet count ≤ 100K/mm ³ **
≤ 50 K/mm ³	Permanently discontinue Study Drug	Monitor daily until 2 successive values show improvement, then monitor every 2-3 days until 2 successive values are > 75K/ mm ³ . Patient should be evaluated by a hematologist to provide diagnostic and therapeutic management Steroids recommended*. It is strongly recommended that, unless the patient has a medical contraindication to receiving glucocorticoids, the patient receives glucocorticoid therapy to reverse the platelet decline. Monitor triglyceride levels weekly and continue AE monitoring during steroid therapy. Discontinue antiplatelet agents/NSAIDS/anticoagulant medication while platelet count <50K/mm ³ if

		possible Obtain additional lab tests if 1 occurrence of platelet count $\leq 100\text{K}/\text{mm}^3$ **
--	--	---

*Recovery in platelet count may be accelerated by administration of high dose steroids. Treatment guidelines for immune thrombocytopenia (Provan et al. 2010) recommend Dexamethasone 40 mg daily for 4 days every 2-4 weeks for 1-4 cycles; Prednis(ol)one 0.5-2 mg/kg/d for 2-4 weeks then taper; or Methylprednisolone 30 mg/kg/day for 7 days (**note:** may require continuation with oral steroids after methyl prednisolone)

**See Appendix J

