Contact study staff if you have any questions or concerns

Site staff are trained to help answer your questions and advise on how to alleviate any discomfort, if needed.

Version 1.0: 01FEB2016

Appendix J: Labs which may be performed in the Event a Platelet Count is Less Than the Lower Limit of Normal (x 2) or < 100,000/mm³ (x 1)

In patients who have any 2 occurrences of platelet count less than the lower limit of normal or who have any 1 occurrence of platelets <100,000/mm³

Note: The actual labs that may be performed are subject to the PI's decision and may change as we learn what the cause of the low platelets are.

To Be Performed at Local Lab
Peripheral smear (should be performed locally, fixed and sent to central lab for review) Fibrinogen split products or D-dimer on fresh blood
To Be Performed at Central Lab
Citrated sample for platelets Coagulation panel (PTI/INR, aPTT)
CBC with reticulocytes
Folate (folic acid)
Vitamin B12
Fibrinogen
von Willebrand factor
Total globulins, total IgA, IgG and IgM
Complement: total C3, total C4, 8b, C5a
hsCRP
Helicobacter pylori (breath test)
Serology for:
H8V, HCV, HIV (if not done recently for screening)
Rubella
CMV
EBV
Parvo 819
Auto-antibody screen:
Antiphospholipid
Rheumatoid factor
Anti-dsDNA
Anti-thyroid
Auto-antibody screen:
Antiphospholipid
To Be Performed at Specialty Lab(s)
Antiplatelet antibodies and Anti-PF4 assay
Anti-ASO antibody

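### The platelet limits in exclusion 8f and in the percutaneous liver-biopsy rule count the thousands twice, so both are printed 1,000 times too high

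*Combined protocol and SAP*

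**What the plan says.** Two rules outside the dosing section set a platelet limit.

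- **Entry.** Section 3.2, item 8f, lists as an excluding laboratory value: "Platelet count below 140,000 K/uL".
- **Biopsy.** Section 6.4.2, item 11, states that "Platelet count will be obtained prior to percutaneous liver biopsy" and that the biopsy does not go ahead if the count is low, which it defines as "Platelets < 75,000 k/uL".

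Section 7.6.3 sets the dosing, monitoring and stopping rules for low platelets. Its text uses full counts, for example "In the event of a confirmed platelet count less than 75,000/mm³". Its table uses K: the top row is "Normal range, >140K/mm ³", and the restart condition after a pause begins "When platelet count returns to >100K/mm". The appendix on additional labs for low platelets (headed Appendix J in the body, listed as Appendix K in the contents) returns to full counts and covers patients "who have any 1 occurrence of platelets <100,000/mm³".

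Nothing in the protocol gives K a different meaning or corrects either limit.

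**The concern.** Both limits combine a number already written out in thousands with a unit that multiplies by a thousand again. Each one decides something: the first decides who may be randomized, and the second decides whether an invasive procedure is done. Applied as printed, no patient could enter and no percutaneous biopsy could be performed.

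Platelets are also a central safety measure in this trial. Section 2.3.4 reports a mild fall in platelet count with the drug, Section 6.4.5 requires weekly counts, and Section 7.6.3 sets out graded actions. Section 7.1.3 provides for monitoring of compliance with the protocol, and Section 7.8 makes a violation of entry criteria a reason for withdrawal. The wording of an entry limit is therefore what conduct is audited against.

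**Working it through.** **Step 1: what K means here.** Three levels appear in both notations.

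| Level | Full count | K notation |
|---|---|---|
| Dose pause | below 75,000/mm³ (7.6.3 text) | 50K to 75K/mm³ row (7.6.3 table) |
| Recovery before dosing resumes | at least 100,000/mm³ (7.6.3 text) | above 100K/mm³ (7.6.3 table) |
| Additional labs after one low count | below 100,000/mm³ (labs appendix) | at or below 100K/mm³ (7.6.3 table) |

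The inequalities at the boundary differ slightly in the last two rows, but the numeric level is the same in each pair. Hence K = 1,000.

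**Step 2: volume units.** 1 uL = 1 mm³, so no further conversion factor enters.

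**Step 3: the printed limits, read literally.**

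- Exclusion 8f: 140,000 × 1,000 = 140,000,000/uL.
- Biopsy rule: 75,000 × 1,000 = 75,000,000/uL.

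**Step 4: comparison with the matching levels in Section 7.6.3.**

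- Lower edge of normal: 140K/mm³ = 140 × 1,000 = 140,000/mm³. Ratio: 140,000,000 / 140,000 = 1,000.
- Dose-pause limit: 75,000/mm³. Ratio: 75,000,000 / 75,000 = 1,000.

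**Step 5: drop the extra K.** Exclusion 8f becomes 140,000/uL, ratio 140,000 / 140,000 = 1. The biopsy limit becomes 75,000/uL, ratio 75,000 / 75,000 = 1. In both places the digits already printed are the intended count, and only the K is surplus.

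**The case against.** The strongest reply is that this is a slip of notation with only one sensible reading. A limit of 140 million per uL is impossible, so no site would apply it, and the printed digits show what was meant. Section 7.14 refers to five enrolled patients who were treated, so the literal reading was evidently not used at screening, assuming 8f was worded this way when they entered. The direction is also safe: an over-large limit turns patients away or cancels a biopsy, and does not admit or expose anyone at risk. The biopsy is optional and its histology is an exploratory outcome. All of this stands, and it is why the point ranks as minor.

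Two further cautions are fair.

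- Section 7.6.3 governs dosing, not entry or biopsy. The comparison is therefore of equal numeric levels, not of one rule restated. It is needed only to fix the meaning of K and to show that the corrected values are levels the protocol already uses.
- Section 7.6.3 is not free of loose notation itself. Its text once omits the slash in a 75K limit and once doubles the inequality at 50K. Neither slip changes the size of a limit.

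None of these points makes the two printed limits correct.

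**Conclusion.** The point holds. Exclusion 8f and the percutaneous-biopsy rule are each printed at 1,000 times the intended value: 140,000,000 against 140,000 per uL, and 75,000,000 against 75,000 per uL. The conclusion rests on K meaning thousand, which the protocol's own paired notations show. It also rests on the intended limits being the printed digits without the K, which the levels in Section 7.6.3 support.

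This is an error of unit notation in two operative limits, not a miscalculation in the design. The practical risk is low. Sample size, power, randomization and the planned analyses do not depend on it. Severity: minor.

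**What to change.** In Section 3.2, item 8f, print 140,000/mm³ (equivalently 140 K/uL). In Section 6.4.2, item 11, print 75,000/mm³ (75 K/uL). Using mm³ in both places keeps the notation in line with Section 7.6.3.

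The cost is a wording change in two places at the next amendment. No test, visit, sample size or analysis changes.
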